10.1. Schedule of Events

After proper administration and signing of the IC and Research Authorization Forms, all potential subjects will be assessed for study eligibility based on the Inclusion and Exclusion Criteria. Inclusion and Exclusions data as well as limited demographic information will be captured in the subject CRFs.

A ***retrospective review*** of the subject's medical chart will be performed to gather and report data on subject surgical history, reportable AEs from the time of implantation to time of chart review, previous QOL scores, and previous audiometric testing results for Alpha 2 and/or Alpha 2 MPO processors.

An ***in-office visit*** will be conducted with an ENT physician and Audiologist, ideally on the same day, where the following assessments will take place:

ENT Visit:

The ENT visit will consist of an examination of the ear and implant site for skin complications (according to the *Holger Skin Evaluation Index* in Table 2) or other potential AEs (see Section 12 for reportable AEs). The ENT Visit CRF will detail findings (such as erythema, scar, etc.) as well as complications (skin loss, infection, etc.). Any such complications will be recorded on an AE form.

Sophono system satisfaction and QOL questions shall also be administered to allow the subjects' perceived benefits to be assessed. The QOL assessment will be done using the APHAB Version A.

Table 2. Holger Skin Evaluation Index

The skin directly over the implant site will be evaluated on the Holger Skin Evaluation Index.

Holger Skin Evaluation Index
0 = No irritation. Epithelium debris removed if present.
1 = Slight redness, local treatment.
2 = Red and slightly moist tissue. No granuloma formation noted. Local treatment. Extra controls.
3 = Status as in 1 and 2 but local revision became necessary.
4 = Removal of skin-penetrating implant necessary due to infection.
R = Removed implant for reasons not related to skin problems.

Audiology Visit:

All audiometric testing equipment should be calibrated and tested to American National Standards Institute (ANSI) standards, in good repair and functioning well.

All tests should be performed in the order presented in Table 3. Subject will be blinded to processor order.

In sound field testing the good ear should be plugged using an ear plug. The speech presented should be a recording. When results indicate the need for masking, effective masking should be presented in the non-test ear through the use of inserts or headphones using speech weighted noise. Testing should be performed on the affected ear unless otherwise noted.

All audiometric testing shall include aided and unaided testing since completing basic pure tone and speech audiometry in the unaided and aided condition allows functional gain measurements to be made.

This document is electronically controlled. Printed copies are considered uncontrolled.

Confidential

Unaided

1. Audiometry thresholds should be obtained for **both** ears at the following frequencies:
 - Basic Audiometry (inserts or headphones) AC: 250, 500, 1000, 2000, 3000, 4000 & 8000 Hz
 - BC: 500, 1000, 2000, 3000 & 4000 Hz
2. Speech Reception Threshold should be conducted using spondee words. The speech presented should be a recording.
3. Word Recognition should be conducted using *one* NU-6 list for each test. The speech presented should be a recording. The standardized monosyllabic word list should be presented at **65 dBHL** (Hearing Level).
4. Hearing in Noise Testing (HINT) should be conducted using the BKB-SIN. Recording is presented via a single loudspeaker **in the sound field**.

Recorded testing should have babble and speech presented from the same speaker **at 70 dBHL** with the subject 1 meter from speaker at 0° azimuth.

Aided

1. Audiometry thresholds should be obtained at the following frequencies:
 - Aided (sound field): 500, 1000, 2000, 3000 & 4000 HzProcessors should start at 100% optimization and only be lowered if feedback is intolerable for subject.
2. Speech Reception Threshold should be conducted using spondee words in the sound field. The speech presented should be a recording.
3. Word Recognition should be conducted using *one* NU-6 list for each test in the sound field. The speech presented should be a recording. The standardized monosyllabic word list should be presented at **65 dBHL**.

This document is electronically controlled. Printed copies are considered uncontrolled.

Confidential

4. HINT should be conducted using the BKB-SIN. Recording is presented via a single loudspeaker in the sound field.

Recorded testing should have babble and speech presented from the same speaker at **70 dBHL** with the subject 1 meter from speaker at 0° azimuth.

[figure not shown]

Figure 2. Study Flow Chart

This document is electronically controlled. Printed copies are considered uncontrolled.

Confidential

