6.2.1.2. Primary Efficacy Endpoint

The primary efficacy endpoint is the difference (gain) in the free-field pure tone audiometry assessed by pure tone average (PTA) unaided (AC) and aided (BC) by the Alpha 2 MPO processor.

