5.3 Overall study design and plan-description

After informed consent is collected, the study will consist of a retrospective medical chart review to collect data on AEs for all subjects. A prospective clinic visit for subjects still implanted with the Sophono implant will be conducted to evaluate the subject's implant site and conduct hearing tests, along with a QOL and satisfaction self-assessment.

All subjects will be screened for study eligibility. A qualified member of the investigational site's research team will review the inclusion and exclusion criteria to screen each subject. Subjects will be considered enrolled into the study when they have both:

[figure not shown]
- Been informed of the study design, objectives, risks and benefits
- Confirmed interest in participation by signing an IC and Research Authorization Forms

Any subject who currently has or who has had the Sophono implant (including those who have been explanted) may be enrolled.

A Screening and Enrollment Log will be maintained for all subjects. For screen-fail subjects, a reason for failure will be noted.

Clinical data will be collected during:

- a retrospective review of the subject's medical chart will be performed to gather and report data on subject surgical history, reportable AEs from the time of implantation to time of chart review, previous QOL scores, and previous audiometric testing results for the Sophono processors.
- an in-office ENT exam will be conducted to gather and report data on the ear and implant site for skin complications, potential AEs and Sophono system satisfaction and QOL questions. During the in-office visit Audiology testing will be performed to collect data on: Basic Sound Field Audiology thresholds at octave intervals, Speech Reception Threshold, Word Recognition Thresholds and Hearing in Noise.

Figure x – Flow Chart

Data collection requirements are summarized in the following table:

Table x – Data Collection Requirements

Data	Baseline	Retrospective	Prospective	Study Exit
Informed Consent	X			
Inclusion/Exclusion Criteria Evaluation	X			
Demographic	X			
Medical History (including Procedure)	X	X		
Audiogram		X	X	
Speech Recognition Threshold		X	X	
Word Recognition Threshold		X	X	
Quality of Life Scores (including Additional Items)		X	X	
Product Satisfaction			X	
ENT Exam			X	
Adverse Events		X	X	X
Protocol Deviations	X		X	X

6 Determination of Sample Size

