PTA (dB)	The PTA will be calculated as average of the derived audiogram Hz values. For the AC test all the available values at 250Hz, 500Hz, 1000Hz, 2000Hz, 3000Hz, 4000Hz and 8000Hz will be considered in the calculation. For the BC or Aided tests all the available values at 500Hz, 1000Hz, 2000Hz, 3000Hz and 4000Hz will be considered in the calculation. Missing or VT values will not be considered in the calculation.
Gain (dB) in the free-field pure tone audiology	Absolute difference between PTA values
Time to first AE (days)	Study Evaluation- First AE occurrence date ¹
Total time in hospital (days)	Discharge date – Admission date

¹ if more than one procedure or event, consider the date of the first one.

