7.10.1 Primary endpoint

The primary safety endpoint is the proportion of AEs related to the Sophono implant or surgery, which will be assessed through retrospective surgical chart review and prospective ENT exam. The primary safety endpoint will be evaluated on FAS. The AEs used for this endpoint are according to Investigator's determination of the event's relatedness to the device or surgery.

Adverse Event rates will be displayed together with their 95% confidence interval (95%CI) overall, by site and by type of event.

A time to first Adverse Event will be performed using survival analysis. The analysis will be supported by a Kaplan Meier curve indicating the number of patients at risk and any possible comparison of curves between groups will be done using the Log-Rank Test where appropriate.

Table x - Primary safety endpoint – Sophono Implant related Adverse Events rates

Figure x - Kaplan Meier estimate of first Sophono Implant related Adverse Event occurrence

Table x - Kaplan Meier estimate of first Sophono Implant related Adverse Event occurrence

The primary effectiveness endpoint is the absolute difference (gain) in the free-field pure tone audiometry assessed by PTA unaided (AC) and aided by the Alpha 2 MPO processor. The primary effectiveness endpoint will be evaluated on PPS.

The difference between unaided and aided measurements will be analyzed by means of paired (samples) t-test or Wilcoxon signed rank sum test according to the normal or non-normal distribution.

Additional analysis will be performed on:

- the "within indication" subset will exclude from the analysis subjects whose Prospective AC & BC tests do not meet the device indications for use.

- The subsets defined by implanted ear diagnosis. For the subject affected by SSD, analyses will be performed for both the derived variables (both NR substitution methods).

Table x - Primary effectiveness endpoint - Difference in PTA between unaided (AC) and aided by the alpha 2 MPO Processor (Audiogram Results Gain)

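### The primary gain is called free-field, but the procedure pairs headphone unaided thresholds with aided sound-field thresholds taken with the good ear plugged, so it mixes the processor with a change of test condition

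*Protocol*

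**What the plan says.** SAP 7.10.1 defines the primary effectiveness endpoint as the "absolute difference (gain) in the free-field pure tone audiometry assessed by PTA unaided (AC) and aided by the Alpha 2 MPO processor". Protocol 6.2.1.2 gives the same definition and tags the aided term BC.

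Protocol 10.1 sets out how the two terms are obtained:

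- Unaided tones, both ears: "Basic Audiometry (inserts or headphones) AC: 250, 500, 1000, 2000, 3000, 4000 & 8000 Hz".
- Aided tones: sound field, at 500, 1000, 2000, 3000 and 4000 Hz.
- Non-test ear: "In sound field testing the good ear should be plugged using an ear plug". Also, "When results indicate the need for masking, effective masking should be presented in the non-test ear".
- Purpose: testing in the "unaided and aided condition allows functional gain measurements to be made".

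The only unaided test that 10.1 explicitly places in the sound field is BKB-SIN.

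SAP 7.6 builds the unaided average from the headphone test: "For the AC test all the available values at 250Hz, 500Hz, 1000Hz, 2000Hz, 3000Hz, 4000Hz and 8000Hz will be considered in the calculation". The aided average uses the five frequencies from 500 to 4000 Hz. No correction for transducer, plug or frequency set is planned.

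Two places point the other way. SAP 5.3 describes the visit audiometry as "Basic Sound Field Audiology thresholds at octave intervals", and Table 3 in Protocol 10.5 makes a run without a processor Test 1 of the audiogram design. The Synopsis lists baseline AC thresholds without naming a transducer.

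**The concern.** A functional gain isolates the processor only if the aided and unaided thresholds are taken under the same conditions. Here the transducer changes between the two terms, and so does the state of the non-test ear. The plug rule covers sound-field testing only, so a plugged good ear can affect the aided term and not the unaided one. With one near-normal ear, as in SSD and unilateral loss, that ear may respond to the loudspeaker through the plug, and the response would be credited to the processor. No unaided run with the same plug is listed from which to estimate that contribution.

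At stake is the primary effectiveness estimate, and whether it can be reported as free-field functional gain.

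**Working it through.** **1. The plan's own figure.** Protocol 13.1 uses 58.7 (SD 8.2) dB HL unaided and 29.7 (SD 8.2) aided, so the planned gain is 58.7 − 29.7 = 29.0 dB. It states 6 pairs at two-sided 5% and 95% power. For a paired t-test the SD of the difference is 8.2 × √(2(1 − ρ)), and ρ is not given.

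| ρ | SD of difference (dB) | Pairs needed |
|---|---|---|
| 0.5 | 8.2 | 4 |
| 0 | 11.6 | 5 (power 0.982; 0.997 with 6) |
| −0.5 | 14.2 | 6 (power 0.975) |

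The stated 6 is adequate over this range and needs no change. It does not bear on this point, because sample size cannot remove a systematic offset.

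**2. The two terms side by side (Protocol 10.1, SAP 7.6).**

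| | Unaided term | Aided term |
|---|---|---|
| Delivery | Inserts or headphones | Sound field |
| Good ear | No plug rule; masked if indicated | Plugged; masked if indicated |
| Frequencies averaged | Seven, 250–8000 Hz | Five, 500–4000 Hz |
| Processor | None | Alpha 2 MPO |

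Only the last row should differ.

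**3. Direction of the plugged-ear effect.** Let U be the unaided average, D the aided threshold through the device alone, and P the threshold of the plugged ear. If the subject responds by the more sensitive route, the recorded gain is U − min(D, P). The excess over U − D is max(0, D − P), which is never negative. This part of the bias can only favour the device. The same argument says nothing about the transducer.

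**4. Size at the planned aided value.** P is the hearing-ear threshold plus the plug attenuation. The SSD indication in the Synopsis requires a hearing ear better than 20 dB HL; I take 0–20. Attenuation of 20–35 dB and no masking are assumptions.

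- P runs from 0 + 20 = 20 to 20 + 35 = 55 dB HL.
- With D = 29.7, the largest excess is 29.7 − 20 = 9.7 dB, which is 9.7/29.0 = 33% of the planned gain.
- The excess is zero whenever P is 29.7 or worse.

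**5. Size where the device adds little.** SAP 7.6 (method I) sets an unaided AC no-response without a recorded limit to 100 dB. For an SSD subject with no response at any frequency, a processor adding nothing would record between 100 − 55 = 45 and 100 − 20 = 80 dB. These are limits for one subject under that premise, not expected means.

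**6. Effect on the test.** With zero processor effect, 72 pairs and an assumed SD of the difference of 8.2–11.6 dB, the two-sided 5% paired t-test rejects as follows.

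| Assumed mean offset | Rejection probability |
|---|---|
| 2 dB | 30–53% |
| 3 dB | 58–87% |
| 5 dB | 95–99.9% |

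If the true gain is near 29 dB the test rejects anyway. What suffers then is the estimate and its confidence interval.

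**The case against.** The documents tag the unaided term AC, and SAP 7.6 says which test supplies it. On that reading the intended quantity is collected and only the free-field label is wrong. This stands in part: headphone AC minus aided threshold is measured, but it is not the free-field gain that both definitions name.

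An unaided sound-field run may have been intended. Protocol 10.1 says that all audiometry includes both conditions, Table 3 has a run without a processor, SAP 5.3 speaks of sound-field thresholds, and the flow chart is not available here. This also stands, and it is why the point is a conflict to reconcile and not a proven omission. Sites that follow the numbered list would still not collect the threshold.

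Masking is a real safeguard, and a near-normal ear responding through a plug is an obvious reason to use it. But 10.1 gives no criterion for it. In SSD the device signal must itself be heard by the good ear, so effective masking there would be expected to suppress the device as well.

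SAP 7.10.1 plans subsets by implanted-ear diagnosis and a within-indication analysis. These show SSD separately but keep the headphone term, so they do not supply the missing control.

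Subjects with bilateral implants may have no good ear, and the effect may be small in bilateral conductive loss. The Alpha 2 versus MPO comparison (SAP 7.10.3) is unaffected, since both its terms are aided sound-field thresholds.

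**Conclusion.** The point holds as a conflict over how a component of the primary endpoint is measured, with a bias that can favour the device. Under the assumptions in the working, the inflation is 0 to about 10 dB for a subject at the planned aided threshold. It is larger where the device adds little, notably in SSD with no unaided response. The documents give neither the attenuation nor the extent of masking, so no expected mean bias can be stated.

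Three stronger readings are tempting, and the documents do not support them:

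- **That an unaided sound-field threshold was certainly left out.** SAP 5.3 and Table 3 leave this open.
- **That 4 to 39 dB of the planned 29.0 dB could be spurious (58.7 − 55 = 3.7; 58.7 − 20 = 38.7).** That range takes 58.7 from a series with congenital ear canal atresia and the other ear from the SSD indication. It also presumes no masking and a processor that adds nothing.
- **That the change of transducer also favours the device.** Nothing in the documents gives its sign or size, and Protocol 10.1 requires equipment calibrated to ANSI standards.

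**What to change.** In Test 1 (no processor), record sound-field thresholds at 500, 1000, 2000, 3000 and 4000 Hz with the same loudspeaker, plug and masking as Tests 2 and 3. Amend Protocol 10.1 and SAP 5.3, 7.6 and 7.10.1 so that the unaided average uses these five values. This also removes the mismatch of seven against five frequencies. The cost is a few extra minutes in a session that already runs unaided BKB-SIN from a loudspeaker.

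If visits are complete:

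- Restate the endpoint as headphone AC minus aided sound-field threshold.
- Compute both averages on the shared frequencies from 500 to 4000 Hz.
- Report SSD separately.
- Do not call the result free-field functional gain.

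This needs a change of wording and a revised PTA derivation but no new data. It leaves any plugged-ear contribution unmeasured, and the report should say so.

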10.2. Subject Screening

Sites will have a log of all patients at their Institution who have been implanted with the Sophono implant, including those who have been explanted. All subjects will be contacted for interest in study participation and asked to sign the IC and Research Authorization Form for retrospective medical chart review as well as a prospective data collection visit. Any subject's unwillingness to participate will be documented in the Subject Screening/Enrollment Log.

10.3. Prior and Concomitant Medications

No change in medication is required for this study, nor will any additional medications be required. Medications will not be collected unless relevant to an AE.

10.4. Subject Consent

Prior to study enrollment and before any study visits are initiated, all subjects must document their consent by signing an IC and Research Authorization Form. The Study Investigator or his/her authorized designee will conduct the informed consent process during which the subject will have the opportunity to ask questions and receive answers about the study. Subjects will be made aware that the study includes a medical chart review, as well as an in-office follow-up visit, and they should be willing to comply with the study requirements to be available for study visits. If they decide not to come in for the in-office follow-up visit the data from the medical chart review will still be used in data analysis.

A copy of the signed IC and Research Authorization will be provided to the subject, and the original signed version will be retained in the site's study files. The site will record the date of consent in the CRFs.

Obtaining data from a subject's medical chart or a follow-up visit without obtaining informed consent is a protocol violation and is to be recorded in the Protocol Deviation CRF and reported to the Sponsor, as well as the respective IRB/IEC as soon as possible, **but no later than five (5) working days after the event occurred, or sooner if required by the IRB/IEC.**

10.5. Randomization and Treatment Assignment

There is no randomization in this study as bias is expected to be negligible. All subjects will undergo testing with two (2) processors and a blank in the order given below (Table 3).

This document is electronically controlled. Printed copies are considered uncontrolled.

Confidential

Table 3. Audiogram Test Design

Tests	Subject has Alpha 1, Alpha 2, or Alpha 2 MPO Processor
Test 1	No processor
Test 2	Alpha 2
Test 3	Alpha 2 MPO

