Study Procedures and Assessments	
After proper administration and signing of the Informed Consent (IC) and Research Authorization Forms, all potential subjects will be assessed for study eligibility based on the Inclusion and Exclusion Criteria.
 
Retrospective data collection from medical charts for safety and baseline data will be collected by the site.
 
Prospective Data Collection (visit):
 
• ENT visit
• Examination of implanted ear• Satisfaction Questions• QOL questions: Abbreviated Profile of Hearing Aid Benefit (APHAB)TM Version A• Audiologist Visit: Optimization of device programming for all aided tests should be completed.
• Hearing in Noise Test: BKB-SIN• Speech and Language Tests: Word Recognition Score, Speech Reception Threshold• Audiograms:
• Baseline AC Thresholds at octave intervals at 250, 500, 1000, 2000, 3000, 4000 and 8000 Hz• Test Baseline BC and Aided Thresholds at 500, 1000, 2000, 3000 and 4000 Hz• Subjects are blinded to processor types for all tests

This document is electronically controlled. Printed copies are considered uncontrolled.

Confidential

	
Audiogram Test Design
 
  
 Tests	Subject has Alpha 1, Alpha 2, or Alpha 2 MPO Processor*	
   
 Test 1	No processor	
 
 Test 2	Alpha 2	
 
 Test 3	Alpha 2 MPO	
  
 
*Alpha 2 and Alpha 2 MPO processors will be provided to each site for use in the study. Thus, regardless of the processor the subject wears daily, both Alpha2 and Alpha 2 MPO can be tested on each subject.
	Tests	Subject has Alpha 1, Alpha 2, or Alpha 2 MPO Processor*	Test 1	No processor	Test 2	Alpha 2	Test 3	Alpha 2 MPO
Tests	Subject has Alpha 1, Alpha 2, or Alpha 2 MPO Processor*								
Test 1	No processor								
Test 2	Alpha 2								
Test 3	Alpha 2 MPO								

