6.2.2. Secondary Endpoints

The secondary endpoints include:

- The difference in the free-field pure tone audiometry assessed by PTA aided by Alpha 2 processor compared to the PTA aided by Alpha 2 MPO processor
- Change over time of PTA in the Sophono Alpha 2 and Alpha 2 MPO
- Subject satisfaction, via non-validated satisfaction questions and QOL assessment through validated Abbreviated Profile of Hearing Aid Benefit (APHAB)TM assessment

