13.1. Sample size

Since the primary endpoint is composed of a safety and efficacy endpoint, the sample was determined by the primary objective on safety because it requires the larger sample size. An approximate total of 100 subjects will be enrolled.

Sample size on safety

The sample size calculation was estimated using data from previous studies with a precision-based calculation. (20, 21) Recent data have shown that 15.2% of percutaneous implants are lost in children and adverse skin reactions were found in 7.8 % during follow-up visits. (21) Using this information and assuming a lower incidence of implant loss in transcutaneous devices (19, 22, 23) and a lower incidence of skin reaction (18, 24), a minimum incidence of 14% of any adverse events with a sample size of 72 subjects will be able to obtain a 95% confidence level with a precision of +/- 9% (ranging from 5% to 23%). Considering a 25% withdrawal or potential dropout rate, a total of approximately 100 subjects will be enrolled.

Sample size on efficacy

It is expected that at least 6 paired subjects with the pure tone audiometry evaluation will be needed in order to demonstrate a difference in means between unaided and aided measurements in Hearing Improvement measured as PTA. From a literature search we found that studies have shown an average of 50% improvement on hearing measured as PTA.(13, 20, 21, 25-34) In the paper of Siegert (34) the mean and standard deviation of pure tone audiometry in 21 patients was 58.7 ± 8.2 dB HL unaided and 29.7 ± 8.2 dB HL aided. Based on these values, alpha level 5%, power 95% and two-sided test, a total of 6 paired subjects are needed.

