7.1.3 Analysis Set

The following subject set will be used for the analysis:

- The Full Analysis Set (FAS) includes **all** patients enrolled in the study who sign Patient Informed Consent and fulfill the inclusion and exclusion criteria. The FAS will be used to evaluate the primary safety endpoint.
- The Per Protocol Set (PPS) includes all patients enrolled in the study who sign Patient Informed Consent, fulfill the inclusion and exclusion criteria, and perform prospective activities. The PPS will be used to evaluate the primary effectiveness endpoint and secondary endpoints.

The following table shows how each population set will be used for analyses:

Table x – Analysis steps by population set

Population set	Baseline assessment*	Primary Safety Endpoints	Primary Effectiveness Endpoints	Secondary Endpoints
FAS	✓	✓		
PPS	✓		✓	✓

*According to the clinical study team, baseline assessment on PPS will only be performed after evaluating the difference in sample size of FAS and PPS.

For those patients who drop out of the study, the analyses will include all data up to the point of their last data collection.

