7.10.3 Secondary endpoint#1

The secondary objective#1 will be evaluated as the difference in the free-field pure tone audiometry assessed by PTA aided by Alpha 2 processor compared to the PTA aided by Alpha 2 MPO processor. The difference between Alpha 2 and Alpha 2 MPO measurements will be analyzed by means of paired (samples) t-test or Wilcoxon signed rank sum test according to the normal or non-normal distribution.

Table x - Difference in PTA by device (Audiogram Results Gain)

Figure x - PTA by device type

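### Every subject is tested with Alpha 2 before Alpha 2 MPO, so the processor comparison in secondary endpoint 1 cannot be separated from test order

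*Protocol*

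**What the plan says.** Protocol 10.5 states: "There is no randomization in this study as bias is expected to be negligible." Its Table 3 gives a single order: Test 1 without a processor, Test 2 with Alpha 2, Test 3 with Alpha 2 MPO. Section 10.1 makes the order an instruction to the audiologist: "All tests should be performed in the order presented in Table 3." The Audiogram Test Design table in the Synopsis repeats it. Subjects are blinded to processor type and order, but blinding does not vary the order.

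Comparing the two processors is secondary objective 1 and part of the study aim in Protocol 5.1. The endpoint in Protocol 6.2.2 is the "PTA aided by Alpha 2 processor compared to the PTA aided by Alpha 2 MPO processor". SAP 7.10.3 says: "The difference between Alpha 2 and Alpha 2 MPO measurements will be analyzed by means of paired (samples) t-test", or a Wilcoxon signed rank test if the data are not normal. Neither analysis has a term for order. SAP 7.2 sets a two-sided 0.05 level. On the population, SAP 7.1.3 says: "The PPS will be used to evaluate the primary effectiveness endpoint and secondary endpoints."

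**The concern.** Aided thresholds are behavioural responses. They are collected in a visit that also includes speech reception, word recognition and speech-in-noise testing, unaided and aided (Protocol 10.1). A subject may do better on a later test through practice, or worse through fatigue. Because MPO is always last, practice would favour MPO and fatigue would count against it.

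With one sequence, a significant Alpha 2 versus MPO difference could come from equal processors, and a real difference could be hidden. A larger sample would only estimate the mixture more precisely. A covariate cannot help, because position does not vary. The retrospective audiograms are assigned to the change-over-time endpoints (SAP 7.10.4 and 7.10.6), so no planned analysis provides a check.

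**Working it through.** **No plan figure to reproduce.** The documents state no effect size, SD, power or sample size for secondary endpoint 1.

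**Structure.** Let τ be the true MPO minus Alpha 2 difference in aided PTA, and π the shift from Test 2 to Test 3. In the fixed sequence every subject's paired difference has mean τ + π. The data hold one mean and two unknowns, so τ is not identifiable. The Wilcoxon test has the same problem.

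**Inputs for an illustration**
- Level: two-sided 0.05 (SAP 7.2).
- n = 72: the evaluable number in Protocol 13.1. It was set for safety precision and is borrowed here. n = 36, half of it, is an arbitrary lower case. The number with both aided tests may fall below 72, because explanted subjects have no prospective visit.
- Single-measurement SD: 8.2 dB, from the published figures "58.7 ± 8.2 dB HL unaided and 29.7 ± 8.2 dB HL aided" in Protocol 13.1.
- Paired SD: not given for two aided tests, so assumed. With within-subject correlation ρ, SD = 8.2 × √(2(1 − ρ)). ρ = 0.814 gives 5.0 dB, ρ = 0.5 gives 8.2 dB and ρ = 0 gives 11.6 dB.
- Order shift π: not given, so assumed to be 1 or 2 dB.

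**Probability of p<0.05 when the processors are equal (τ = 0).** This is the noncentral t probability with n − 1 degrees of freedom and noncentrality π√n/SD. For example, π = 1, SD = 5 and n = 72 give 1 × 8.485/5 = 1.697 and a probability of 0.388.

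| n | π (dB) | SD 5 | SD 8.2 | SD 11.6 |
|---|---|---|---|---|
| 72 | 1 | 39% | 18% | 11% |
| 72 | 2 | 92% | 53% | 30% |
| 36 | 1 | 21% | 11% | 8% |
| 36 | 2 | 65% | 30% | 17% |

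**Masking.** This is the same arithmetic read the other way. A true 2 dB MPO benefit opposed by 1 dB of fatigue leaves a net 1 dB. At n = 72, power falls from 92%, 53% or 30% to 39%, 18% or 11%.

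**Primary endpoint.** The planned difference is 58.7 − 29.7 = 29 dB. A total shift of 1 to 2 dB is 1/29 = 3.4% to 2/29 = 6.9% of that. Tests 1 and 3 are two positions apart, however. If the shift accrues at each step it is 2 to 4 dB, or 6.9% to 4/29 = 13.8%. Either way it is small beside the planned difference.

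**With the order randomised.** With Alpha 2 first the mean difference is τ + π, and with MPO first it is τ − π. The average of the two sequence means is τ, free of π. With 36 subjects per sequence and pooled SD s, its standard error is (s/2) × √(1/36 + 1/36) = s/√72. That equals the paired-test standard error, with 70 degrees of freedom instead of 71. A simulation of 20,000 runs with order effects of 1 to 2 dB gave rejection rates of 0.049 to 0.051 under no true difference. Power for a true 2 dB difference with a 1 dB order effect was 0.917, 0.534 and 0.295. A paired test with no order effect has 0.917, 0.533 and 0.303.

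**The case against.** The strongest reply is that nothing in the documents shows the order effect to be material. The shifts and paired SDs are assumed, n = 72 comes from the safety calculation, and the results run from 8% to 92%. That range cannot tell a trivial problem from a serious one. This is fair, and it is why the figures are offered as possibilities only.

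There is also mitigation. Subjects are blinded, which limits expectation bias. Before any aided test they complete unaided thresholds at 7 air-conduction and 5 bone-conduction frequencies in both ears, so (7 + 5) × 2 = 24 thresholds, plus speech tests. Much early task learning should therefore fall on Test 1, which would reduce practice gains from Test 2 to Test 3. It does nothing about fatigue, and it does not separate position from processor.

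Finally, the endpoint is secondary, has no stated power, and sits in a post-market study sized for safety. That argues for a recommended change rather than an essential one. It does not support the statement that bias is negligible, for which the protocol gives no data or argument.

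**Conclusion.** The concern holds. In the prospective aided tests, processor and test position are fully confounded for secondary endpoint 1. This follows from the design alone and needs no numerical assumption.

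The practical size is unknown. It depends on an order effect and a paired SD that the documents do not give, and practice and fatigue could partly cancel. Under the assumptions above, a shift of only 1 to 2 dB raises the chance of a false processor difference from 5% to between 8% and 92%, and can equally hide a real one. The primary MPO-versus-unaided contrast has the same structure but is little affected, given its 29 dB planned difference. This should be changed, but it does not threaten the primary analysis.

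**What to change.** Keep the unaided test first. Randomise the order of Tests 2 and 3 in a 1:1 ratio within site, and record the order used on the CRF. Analyse Alpha 2 versus MPO aided PTA as a two-period crossover with a period term. State the assumption that carry-over does not differ between the sequences; these data cannot test it well. Amend the Synopsis test table, Protocol 10.1, Protocol 10.5 with Table 3, and SAP 7.10.3 to match.

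The cost is an allocation list, one CRF field, the text edits, slightly more care by the audiologist, and IRB review of the amendment (Protocol 15.5) at up to 15 sites. The number of tests is unchanged and no extra devices are needed: the Synopsis already notes that "regardless of the processor the subject wears daily, both Alpha2 and Alpha 2 MPO can be tested on each subject". The period term costs one degree of freedom and essentially no power.

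The documents do not say how far testing has progressed, although SAP 10.1 cites a table specification dated 27 April 2018. If testing is complete, withdraw the statement that bias is negligible, report the order confounding as a limitation of secondary objective 1, and do not attribute an observed difference to the processor alone.
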